## 8.2 Handling of missing data and outliers

### 8.2.1 Imputation of efficacy endpoints

For the primary endpoint (treatment success by Day 15), patients who discontinue study treatment (or discontinue the study if randomized to standard of care) prior to Day 15 and had IMV or ECMO on their last assessment by the time of study treatment discontinuation, will be considered not having achieved treatment success by Day 15. Patients discontinuing prior to Day 15 without ever having initiated IMV/ECMO, will be considered having achieved treatment success by Day 15. Patients discontinuing prior to Day 15 due to having significantly improved will be considered having achieved treatment success. Patients who died by Day 15, have not achieved treatment success regardless of IMV/ECMO use by Day 15.

For statistical analyses of change-from-baseline efficacy endpoints at Day 15, the last observation carried forward (LOCF) approach will be used to impute missing data, using the last post-baseline observation available for each patient.

For other efficacy presentations no imputation will be performed, i.e., all presentations will be based on observed data.

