### **3.4 Study endpoints**

#### **3.4.1 Primary efficacy endpoint**

The primary endpoint is treatment success, defined as not requiring any of the following by Day 15:

- Invasive mechanical ventilation (IMV), or
- Extracorporeal membrane oxygenation (ECMO).

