### **8.5 Derived and computed variables**

#### **8.5.1 Treatment success**

Treatment success is achieved for patients not requiring IMV or ECMO by Day 15. If IMV or ECMO is required at any visits prior to Day 15/date of early discontinuation, but no longer required at Day 15/date of early discontinuation, treatment success has been achieved. If IMV or ECMO is not initiated during the study, treatment success has been achieved. As stated in Section 8.2.1, patients who discontinue study treatment (or discontinue the study if randomized to standard of care) prior to Day 15 and had ECMO or IMV on their last assessment by the time of study treatment discontinuation, will be considered not having achieved treatment success by Day 15. Patients who discontinue prior to Day 15 without ever having initiated IMV/ECMO, have achieved treatment success by Day 15. Patients discontinuing prior to Day 15 due to having significantly improved will be considered having achieved treatment success. Patients who died by Day 15, have not achieved treatment success regardless of IMV/ECMO use by Day 15.

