## **9 Patient disposition**

The number and percentage of patients who were enrolled, randomized, who initiated and who completed or discontinued treatment early, together with the reasons for discontinuations, will be presented by treatment group. The number of patients in the All Treated population will be presented.

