## **12 Efficacy analyses**

### **12.1 Primary efficacy endpoint**

For the analysis of the primary endpoint, each of the two pairwise comparisons, emapalumab/anakinra versus standard of care, at both the end of Stage 1 and at the end of Stage 2, will be undertaken using Fisher's exact test comparing the proportion of patients with treatment success.

The null and alternative hypotheses with respect to the primary endpoint are defined as:

$H_0: P_{\text{treatment}} = P_{\text{SoC}}$

$H_A: P_{\text{treatment}} > P_{\text{SoC}}$

where P is the proportion of patients with treatment success as defined for the primary endpoint. The one-sided p-value from Fisher's exact test will be supplemented by the presentation of one-sided exact [Santner et al 1980] confidence intervals of the differences in proportion between emapalumab/anakinra and standard of care, with confidence coefficients of 97.5% at the end of Stage 1 and 84% at the end of Stage 2. Two-sided confidence intervals of the proportions in each group will also be presented, using the method of Clopper-Pearson [Clopper et al 1934].

The primary analysis will not adjust for the stratification factor glucocorticoid use at inclusion in order to avoid incorrect weights being attributed to any classes of the factors with few data points, particularly at Stage 1. However, a sensitivity analysis of the primary endpoint using exact logistic regression will be performed at Stage 1 and 2. This will allow for conditional testing of the treatment effect given the stratification factor. The results of the analysis will be presented in terms of model-adjusted treatment success rates for each treatment group, and p-values and confidence intervals for the odds ratio of the pairwise comparisons to the standard-of-care arm.

The individual success rate profiles will be displayed in a Swimmer plot with bars representing the time in the study and markers for whether IMV/ECMO was used at each visit. The purpose is to show onset of IMV/ECMO and how it evolves over time in relation to treatment.

The relationship between achieving treatment success/no treatment success and the change in hyperinflammatory parameters will be explored by treatment group in Box-Whisker plots with individual scatter.

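### Early discontinuers who never started IMV/ECMO count as primary-endpoint successes for any reason short of death by Day 15, and the failure rule is tied to drug stop in the active arms but to study exit in standard of care

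*SAP*

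**What the plan says.** The endpoint is defined in SAP 3.4.1: "The primary endpoint is treatment success, defined as not requiring any of the following by Day 15", the two items being invasive mechanical ventilation (IMV) and ECMO. SAP 8.2.1, SAP 8.5.1 and Protocol 7.3.8 then add rules for early discontinuation.

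- **Success, never ventilated:** "Patients discontinuing prior to Day 15 without ever having initiated IMV/ECMO, will be considered having achieved treatment success by Day 15".
- **Success, improved:** "Patients discontinuing prior to Day 15 due to having significantly improved will be considered having achieved treatment success". Because this is a separate rule, the one above must also reach patients who left for other reasons.
- **Success, weaned:** if IMV or ECMO was needed earlier "but no longer required at Day 15/date of early discontinuation, treatment success has been achieved".
- **Failure:** applies to "patients who discontinue study treatment (or discontinue the study if randomized to standard of care) prior to Day 15" who "had IMV or ECMO on their last assessment by the time of study treatment discontinuation".
- **Failure, death:** death by Day 15 is a failure whatever the ventilation history.

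Several Protocol sections bear on this. Section 5.3.3.1 keeps patients in the study after study drug is stopped. Section 5.5.3.1 records the date and time of IMV/ECMO requirement at Visits 1 to 7. Section 5.4.7.2 withdraws from the study a patient who starts one of four prohibited drug classes, for example as rescue for worsening; other rescue leaves the patient in. Section 5.3.3.2 asks for an examination and assessments at withdrawal. It does not require status at Day 15, though it does not prevent its collection.

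On sensitivity, SAP 12.1 says: "However, a sensitivity analysis of the primary endpoint using exact logistic regression will be performed at Stage 1 and 2". That analysis adjusts for the glucocorticoid stratum and leaves the scoring unchanged.

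**The concern.** There are two faults and one drafting slip.

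**Unknown Day 15 status is scored as success.** A patient who worsens, receives a prohibited rescue drug and is withdrawn before ventilation is a success unless known to have died by Day 15. Such withdrawal is informative, and the trial is open label. SAP 8.5.2 censors the same patients in the analysis of time to ventilation, so their outcome is treated as unknown there and as known here.

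**The failure rule has different cut-offs by arm.** The trigger is drug stop in the active arms and study exit in standard of care. Follow-up after drug stop is planned, so the split is avoidable.

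**Drafting.** Protocol 7.3.8 contains a sentence giving success to patients who discontinue before Day 15 without the SAP's condition of significant improvement. Read literally, it conflicts with the failure rule in the same paragraph.

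What is at stake is the primary test. With 18 patients per arm, one reclassified patient can change the conclusion. Both documents say that a Stage 2 result significant at 5% will count as confirmed efficacy and may be used to seek approval.

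**Working it through.** **1. The same course, scored by arm**

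| Course (patient alive at Day 15) | Active arm | Standard of care |
|---|---|---|
| On IMV when study drug stops, stays in the study, weaned by Day 15 | Failure under the discontinuation rule (the weaning sentence in SAP 8.5.1, taken alone, gives success) | No drug to stop; weaned by Day 15 while in the study is a success |
| Drug stopped while not ventilated, first ventilated later and still ventilated at Day 15 | Failure on the more natural reading (never initiated; by Day 15). The cut-off at the date of early discontinuation in SAP 8.5.1 leaves room for success | Failure |
| Prohibited rescue for worsening, withdrawn before ventilation | Success | Success |

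Row 1 works against the active arms. Row 2, on the looser reading, favours them. Row 3 helps whichever arm has more such withdrawals.

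**2. Inputs for the size**

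From SAP 5.1, 6 and 12.1 and Protocol 7.1:
- 18 per arm, taken as 9 + 9
- one-sided Fisher's exact test against standard of care
- Stage 1: efficacy if p < 0.025; binding futility if p > 0.690
- Stage 2: efficacy if p < 0.159
- planned true rates 80% and 50%

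Misclassified shares are assumptions, in percentage points of all patients in the arm. Since 0.05 × 18 = 0.9 and 0.10 × 18 = 1.8, 5 and 10 points are about one and two patients.

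**3. Method**

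With a and c successes out of n per arm, p = P(X ≥ a), where X is hypergeometric (2n patients, a + c successes, n drawn). All binomial outcomes are enumerated, and P(declare efficacy) = P(p₁ < 0.025) + P(0.025 ≤ p₁ ≤ 0.690 and p₂ < 0.159). Misclassification enters by shifting the apparent success rate.

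**4. The plan's own figures**

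- 80% vs 50%: 0.1533 (Stage 1) + 0.5825 (Stage 2) = 0.736 after rounding, against 74% stated.
- 50% vs 50%: 0.0105 + 0.1068 = 0.1173, against 9.7% stated from simulation. That gap is a separate matter; 11.7% is the reference below.

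**5. Scenarios**

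| Misclassification | Apparent active / control | P(declare efficacy) |
|---|---|---|
| *True 50% / 50%* | | |
| None | 50 / 50 | 11.7% |
| Active only, wrongly success: 2.5, 5, 10 points | 52.5, 55, 60 / 50 | 14.9%, 18.6%, 27.5% |
| Active only, wrongly failure: 5, 10 points | 45, 40 / 50 | 6.8%, 3.6% |
| Both arms, wrongly success: 5, 10 points | 55 / 55, 60 / 60 | 11.6%, 11.1% |
| *True 80% / 50%* | | |
| None | 80 / 50 | 73.6% |
| Active only, wrongly failure: 2.5, 5, 10 points | 77.5, 75, 70 / 50 | 67.9%, 62.0%, 49.9% |
| Control only, wrongly success: 2.5, 5, 10 points | 80 / 52.5, 55, 60 | 68.1%, 62.2%, 49.4% |
| 10%, 20% of true failures hidden in both arms | 82 / 55, 84 / 60 | 67.2%, 60.1% |

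In the last row, true failures are 20% active and 50% control. Hiding 10% of them moves 2 and 5 points; hiding 20% moves 4 and 10 points. The harm is unequal because control has more failures to hide.

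**6. One patient**

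At 18 per arm, 13 vs 9 successes gives p = 0.153 (efficacy declared). Moving one patient gives 12 vs 9, p = 0.250, or 13 vs 10, p = 0.244 (not declared in either case). The chance of reaching Stage 2 undecided and finishing one patient from the 0.159 boundary is 0.1084 (would lose) + 0.0772 (would gain), about 19%, at 80%/50%. At 50%/50% it is about 12%.

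**The case against.** The strongest reply has four parts.

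**Status at exit is usually observed.** Protocol 5.3.3.2 asks for an examination at withdrawal, so the rule carries forward an observed state, and a known death by Day 15 overrides it. This is fair, but the gap between exit and Day 15 is unobserved and is filled as success even when the patient left because of worsening.

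**The certain arm difference is narrow and conservative.** It needs an active patient on IMV/ECMO at drug stop who is weaned and alive at Day 15. It costs power and does not create a false claim of efficacy. The route favouring the active arms needs the less natural reading. Standard of care has no study drug to stop, which explains the wording. All of this is right, but it does not justify scoring one course differently by arm when Day 15 status is already to be collected.

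**The large error rates come from one-arm scenarios.** No document supports a particular share. Balanced misclassification leaves false positives at 11.6% to 11.1%, and one-patient fragility would exist in a trial of this size under any scoring. These points stand. The figures show sensitivity and do not forecast bias.

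**Other outputs would expose the problem.** SAP 9 says that patients who "discontinued treatment early, together with the reasons for discontinuations, will be presented by treatment group". There is also a swimmer plot of IMV/ECMO, a time-to-IMV-or-ECMO analysis with censoring, survival, and clinical status over time. They would make a result driven by exits visible. None re-tests the primary endpoint under another scoring rule.

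**Conclusion.** The concern holds and should be fixed before the analysis. The text is clear on both parts: an early discontinuer never on IMV/ECMO is a success for any reason short of death by Day 15, and the failure rule uses a different trigger in the active arms than in standard of care. An arm-dependent scoring rule for the primary endpoint of an open-label trial is an error in the plan, beyond a lack of detail.

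The size is conditional. It rests on assumed shares, 9 + 9 patients per arm and the planned boundaries. About one or two patients misclassified in one arm is enough to move the false-positive rate from 11.7% to between 3.6% and 27.5%, or power from 73.6% to about 50%. With the same share of failures hidden in both arms, false positives do not rise but power still falls to 67.2% or 60.1%. Confidence is high on the reading of the text; the net direction of bias cannot be determined from the documents.

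**What to change.** 1. In SAP 8.2.1 and 8.5.1 and Protocol 7.3.8, score all three arms on observed IMV/ECMO and vital status to Day 15, whether or not study drug was stopped. Keep death by Day 15 as failure and being off IMV/ECMO at Day 15 as success.
2. For patients withdrawn from the study, record IMV/ECMO and vital status at Day 15 where consent allows.
3. Where Day 15 status stays unknown, apply one rule in every arm: on IMV/ECMO at the last assessment before leaving the study is failure; otherwise the present success rule (never ventilated, or weaned before leaving).
4. Add two sensitivity analyses, applied identically in all arms: (i) patients who leave off IMV/ECMO with unknown Day 15 status, other than for improvement or discharge, scored as failures; (ii) a tipping-point analysis over the patients with unknown status.
5. Reconcile the unqualified sentence in Protocol 7.3.8 with the SAP's condition of significant improvement.

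The wording should be settled before the SAP is locked ahead of the Stage 1 analysis, as SAP 5.2 requires of the SAP as a whole.

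The cost is wording changes, a Day 15 status check for withdrawn patients and two analyses; patient care is unchanged. Observed success rates may be slightly lower. Analysis (i) can itself mislead if patients who would have succeeded are scored as failures unequally. With 5 to 10 points in control only, false positives at 50%/50% are 18.6% to 27.5%; with 5 to 10 points in active only, power at 80%/50% is 62.0% to 49.9%. With 5 to 10 points in both arms, false positives are 11.6% to 11.1% and power is 73.3%. It should therefore be read beside the tipping-point analysis and should not replace the primary analysis.

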5.5.3.2 MEWS score

Modified early warning system score (MEWS) will be assessed at Visit 1 (Day 1), Visit 6 (Day 15) and Visit 7 (Day 28) and recorded in the CRF.

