5.5.3.3 SpO₂, PaO₂ and FiO₂

Resting peripheral capillary oxygen saturation (SpO_2) will be measured 3 times per day at Visits 1 to 7, and recorded in the CRF. For Visit 7, if the patient is discharged from the hospital prior to this visit, the SpO₂ will be performed only once at this visit.

The partial pressure of oxygen (PaO_2) and the fraction of inspired oxygen (FiO_2) will be measured at screening, at Visit 6 and Visit 7, and recorded in the CRF.

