### **12.2.2 Change from baseline in MEWs score**

Change from baseline in MEWs score at Day 15/LOCF will be analyzed using analysis of covariance (ANCOVA) including treatment arm as a fixed factor and baseline MEWs score as a covariate. Least square mean changes per group, associated 90% two-sided CI, and p-values for the comparison vs. standard of care, will be presented.

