### **12.2.4 Change from baseline in PaO2/FiO2**

Change from baseline (screening) during treatment by visit will be summarized using descriptive statistics as described in 12.2.3.

Furthermore, change from baseline in PaO2/FiO2 at Day 15/LOCF will be analyzed using ANCOVA as described in 12.2.2.

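### For MEWS and PaO2/FiO2, LOCF has no scheduled value to carry before Visit 6, so the Day 15 ANCOVAs in effect compare survivors, and the SAP gives deaths no place in them

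*SAP*

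**What the plan says.** - **Imputation rule.** SAP 8.2.1, repeated in Protocol 7.3.8, sets the rule for missing Day 15 change-from-baseline values: "the last observation carried forward (LOCF) approach will be used to impute missing data, using the last post-baseline observation available for each patient". A baseline or screening value is not carried.
- **MEWS schedule.** Protocol 5.5.3.2: the score "will be assessed at Visit 1 (Day 1), Visit 6 (Day 15) and Visit 7 (Day 28"). SAP 8.5.3 lists the same three visits.
- **PaO2/FiO2 schedule.** Protocol 5.5.3.3: both components "will be measured at screening, at Visit 6 and Visit 7". SAP 12.2.4 treats screening as baseline.
- **Analyses.** SAP 12.2.2 plans an ANCOVA of the MEWS change at Day 15/LOCF on arm and baseline score. SAP 12.2.4 says that the PaO2/FiO2 change "at Day 15/LOCF will be analyzed using ANCOVA as described in 12.2.2".
- **Deaths.** SAP 8.2.1 and 8.5.1 count death by Day 15 as failure of the primary endpoint. No rule says how a death enters a change-from-baseline analysis.

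**The concern.** The label Day 15/LOCF suggests that every patient contributes a value. For these two endpoints the schedule gives the rule nothing to work on. A patient who dies on, say, Day 9 is a failure in the primary analysis and is simply absent from the MEWS and PaO2/FiO2 models.

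Who survives to be measured can depend on treatment. If one arm keeps more of the sickest patients alive, they enter that arm's mean, while their counterparts in the other arm are missing. Patients who leave hospital early and are not assessed at Visit 6 would also be missing; that removes good outcomes and can push the other way. The randomised comparison is lost in either case.

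Timing adds to this. Protocol 7.3.3.2.1 and SAP 12.2.1 hold overall survival back to the end of follow-up, so the Stage 2 ANCOVAs would be read before the formal survival analysis.

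**Working it through.** **Step 1: what LOCF can use.** The plan states no figure for these two analyses, so there is none to reproduce. The check is of schedule against rule (Protocol Table 2).

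| Endpoint | Baseline | Scheduled at Visits 2 to 5 (Days 4, 7, 10, 13) | Next scheduled value |
|---|---|---|---|
| MEWS | Day 1 | none | Day 15 |
| PaO2/FiO2 | screening | none | Day 15 |
| SpO2, oxygen supplementation, blood gases, laboratory values | Day 1 | all four visits | Day 15 |

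The gap is confined to the first two rows. Vital signs and blood gases are taken at Visits 2 to 5, but neither document plans to derive an interim MEWS or PaO2/FiO2 from them. MEWS also needs the alert/voice/pain/unresponsive item.

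**Step 2: patients lost.** With 18 per arm, the expected loss is 18 × d for an assumed death rate d: 0.9 at 5%, 1.8 at 10%, 2.7 at 15%, 3.6 at 20% and 5.4 at 30%.

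**Step 3: illustrative bias for MEWS. Every input here except the model form is an assumption.**
- Latent Day 15 severity s is standard normal. The Day 15 score is 2 + 1.8s (SD 1.8).
- Baseline MEWS has mean 2, SD 1.2 and correlation 0.5 with s.
- Death occurs when a latent variable with correlation ρ to s exceeds its (1 − d) quantile.
- Treatment has no effect on the score itself.
- The model is the planned one, change on arm plus baseline, fitted to survivors. It was simulated with 400,000 patients per arm, so the Monte Carlo standard error is about 1.8 × √0.75 × √(2/400,000) ≈ 0.0035.

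A hand check is available. Mean severity among survivors is −ρk, where k = φ(z)/(1 − d) and z is the (1 − d) normal quantile. Adjusting for a baseline with correlation 0.5 removes about 0.5² = 0.25 of the difference. So

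bias ≈ 1.8 × 0.75 × ρ × (k_SoC − k_active) = 1.35ρ(k_SoC − k_active).

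For 20% against 10%: k = 0.3500 and 0.1950, difference 0.1550. The bias is 1.35 × 0.5 × 0.1550 = 0.105 at ρ = 0.5 and 1.35 × 0.8 × 0.1550 = 0.167 at ρ = 0.8. For 10% against 5% the k difference is 0.1950 − 0.1086 = 0.0864; for 30% against 15% it is 0.4967 − 0.2743 = 0.2224.

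Positive values mean that the active arm looks worse.

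| Deaths, SoC vs active | ρ | Hand formula | Simulated bias | Simulated estimate if the true benefit is −0.2 |
|---|---|---|---|---|
| 10% vs 5% | 0.5 | 0.058 | 0.062 | −0.139 |
| 10% vs 5% | 0.8 | 0.093 | 0.098 | −0.109 |
| 20% vs 10% | 0.5 | 0.105 | 0.103 | −0.090 |
| 20% vs 10% | 0.8 | 0.167 | 0.175 | −0.025 |
| 30% vs 15% | 0.5 | 0.150 | 0.155 | −0.041 |
| 30% vs 15% | 0.8 | 0.240 | 0.258 | +0.053 |

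With ρ = 0, or with 20% deaths in both arms, the simulated bias lies between −0.006 and +0.004, which is zero within simulation error. No comparable figure was computed for PaO2/FiO2.

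**The case against.** **LOCF is not wholly empty.** This stands. SAP 8.1 admits unscheduled values. Protocol 5.3.3.2 asks for a Visit 6 type assessment at study withdrawal, which would cover patients withdrawn for prohibited rescue therapy (Protocol 5.4.7.2). A Visit 6 on Day 14 is allowed (Protocol 5.5.1.5), falls in the Visit 5 window of SAP Table 2, and could then be carried to Day 15. A reader might infer that LOCF can never fill these endpoints; the documents do not support that. None of these routes reliably covers a patient who dies earlier, however.

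**The consequence is limited.** This also stands. Protocol 7.3.1 makes secondary endpoints descriptive and their p-values exploratory. No stopping or success rule uses MEWS or PaO2/FiO2. Death is counted in the primary endpoint, overall survival, category 1 of the 7-point scale and the death listing.

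**A dramatic example proves little.** Suppose 4 of 18 die on standard of care and 2 of 18 on active treatment, the two extra active survivors change by +3, and every other survivor changes by −1. The means are then (14 × −1 + 2 × 3)/16 = −0.5 against −1.0. That half-point gap comes from inputs chosen without spread and from unadjusted means, whereas the plan adjusts for baseline. With similar death rates, the adjusted model above gives 0.10 to 0.18.

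**Loss through discharge is uncertain.** Protocol 5.5.1.5 does not waive Visit 6 for discharged patients, and Protocol 5.3.3.1 keeps patients who stop treatment in the study. Discharge is a possible route to missing values, not an established one.

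**Conclusion.** The point holds for MEWS and PaO2/FiO2 only. The schedule finding is firm: no post-baseline value is scheduled before Visit 6, and no rule covers deaths in these ANCOVAs. Followed as written, the analysis becomes a comparison of patients with a post-baseline value, in practice mostly survivors.

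The bias is conditional and its size unknown. Under the assumed death rates, SDs and correlations it is about 0.06 to 0.26 MEWS points against the arm with fewer deaths, and about zero with equal death rates or death unrelated to severity. Non-attendance after early discharge could act in the opposite direction, so the net direction cannot be stated in advance.

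A reader might infer that a life-saving arm would be shown as harmful. The documents do not support that: they give no death rates or SDs, and a true 0.2-point benefit changed sign in only the most extreme of the six scenarios with unequal deaths and ρ above zero. Nor is the trial's main conclusion at risk, since the primary endpoint has its own death rule. The change is worth making because the remedy is cheap and the data are already collected.

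**What to change.** Add a separate SAP paragraph for these two endpoints. Leave 12.2.2 as it is, because 12.2.3 to 12.2.5, 12.2.7 and 12.2.8 all refer to it. The paragraph should:

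1. State that LOCF has no scheduled value to use before Visit 6 for MEWS and PaO2/FiO2.
2. Add a rank-based Day 15 comparison: a rank ANCOVA, or a Wilcoxon test stratified by glucocorticoid use at randomisation. Rank death by Day 15 worst, then IMV/ECMO at Day 15 without a value, then patients with observed values in order, and discharged alive without a value best.
3. Give a rule for patients without a value who are alive in hospital and unventilated, or withdrawn: for example, treat them as missing, with a sensitivity analysis.
4. Keep the ANCOVA that Protocol 7.3.3.2.2 names for MEWS, and its PaO2/FiO2 counterpart, labelled as analyses of patients with a post-baseline value. Show beside each the numbers analysed, dead and otherwise missing by arm.

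The cost is SAP wording and modest programming. IMV/ECMO dates (Protocol 5.5.3.1) and survival and discharge (Protocol 5.5.3.8) are already recorded. The downside is that a rank result is less direct than a mean change and overlaps in part with the 7-point scale.
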